4.1.3 Primary Efficacy Analysis

To evaluate the efficacy of etrolizumab during long-term open-label treatment, efficacy will be summarized within the population of patients who enroll into the Study GA28951. All data available up until the clinical cut-off date (CCOD) will be reported. The endpoints to be summarized are described below. Due to the open-label nature of the study, no treatment comparisons will be made.

Concerning missing data and treatment withdrawal imputation, there will be 3 strategies employed, described below.

Hybrid LOCF

Within this strategy, at each visit only patients who had the possibility of reaching the visit will be considered in the analysis for that specified visit. Patients will be deemed evaluable at a visit if it was possible for them to have reached this visit based on their enrollment date and the date of the closure of Part 1 of the study.

- Patients for whom it is not possible to have reached the visit at the time of the clinical cut off are termed non-evaluable and will not be included in the analysis at that visit.
- For evaluable patients with missing data, Last Observation Carried Forward (LOCF) will be used from their most recent available data.

- For evaluable patients who previously withdrew from treatment, they will be imputed as a non-responder until their maximum hypothetical visit (i.e., the maximum visit that they could have attended if they had remained within the study).
 - For visits after a patient's maximum hypothetical evaluable visit, they will be removed from the analysis.

As Observed

Within this analysis only the available data at each visit will be summarized. No imputation will be performed for missing data or treatment withdrawals.

Non-Responder

Within this strategy, at each visit only patients who had the possibility of reaching the visit will be considered in the analysis for that specified visit. Patients will be deemed evaluable at a visit if it was possible for them to have reached this visit based on their enrollment date and the date of the closure of Part 1 of the study.

- Patients for whom it is not possible to have reached the visit at the time of the clinical cut off are termed non-evaluable and will not be included in the analysis at that visit.
- Evaluable patients with missing data will be set as a non-responder.

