- For evaluable patients who previously withdrew from treatment, they will be imputed as a non-responder until their maximum hypothetical visit (i.e., the maximum visit that they could have attended if they had remained within the program).
 - For visits after a patient's maximum hypothetical evaluable visit, they will be removed from the analysis.

Maximum Hypothetical Evaluable Visit

A patient's maximum hypothetical study day (i.e., the maximum visit that they could have attended if they had remained within the study) is calculated as follows:

$$\text{Maximum hypothetical study day} = (15\text{th May } 2022 - \text{Patient's Day 1 OLE enrollment date})$$

For the hybrid LOCF analysis and non-responder analyses, this will impute patients who have withdrawn as non-responders until the 15th May 2022, which was the latest day of dosing reported in the closure of the study announcement. This excludes patients who withdrew from study drug with reason being stated as "study terminated by sponsor" after 15th February 2022, these patients will not be imputed as non-responders and will be considered 'treatment completers' for the efficacy analysis with data included "as observed"

4.1.3.1 Endoscopic Improvement and Remission at Week 108

As endoscopy data is only collected at a common time point of Week 108 during the OLE Study GA28951, the endpoints of endoscopic improvement and remission will be summarized at this time point. These endpoints will be examined overall and also with patients separated by their previous endoscopic improvement status at their latest visit prior to OLE (e.g., at Week 10/14 or Week 54/62/66 in their parent study).

Population: All patients who enrolled into Part 1 of the OLE Study GA28951.

Baseline: The original baseline value from the parent study will be used.

Sub-groups:

- Table outputs: All patients overall and split by prior endoscopic improvement status and their prior aTNF exposure status.

Analysis 1 - Non-responder

Missing Data:

Patients who are non-evaluable at Week 108 (i.e., it is not possible for them to have reached this visit at the time of the clinical cut-off date) will be removed from the analysis. Patients who remain in Study GA28951 Part 1 (OLE) but are missing endoscopy scores will be imputed as non-responders within the analysis, as LOCF is not appropriate when endoscopy data is not collected routinely.

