Intercurrent events: Patients who withdraw during Study GA28951 will be set to non-responders using the composite strategy if they could have reached OLE Week 108 at the time of the clinical cut-off date had they not withdrawn from treatment. This excludes patients who withdrew from study drug with reason being stated as “study terminated by sponsor” after 15th February 2022.

Analysis 2 - As Observed

Intercurrent events: No imputation will be performed for treatment withdrawals

Missing data: If a patient has missing data at a visit, they will be removed from the analysis and no imputation will be performed.

4.1.3.2 MCS Remission at Week 108

As endoscopy data is only collected at a common time point of Week 108 during the OLE Study GA28951, a full MCS score can only be calculated at this visit. Therefore, the endpoint of MCS remission (clinical remission, response?) will be summarized at this time point. These endpoints will be examined overall and also with patients separated by their previous MCS remission status at their latest visit prior to OLE at Week 10/ 14 or Week 54/62/66 in their parent study.

Population: All patients who enrolled into Part 1 of the OLE Study GA28951.

Baseline: The original baseline value from the parent study will be used.

Sub-groups:

- Table outputs: All patients overall and split by prior MCS remission status and their prior aTNF exposure status.

Analysis 1 - Non-responder

Missing Data: Patients who are non-evaluable at Week 108 (i.e., it is not possible for them to have reached this visit at the time of the clinical cut-off date) will be removed from the analysis. Patients who remain in Study GA28951 but are missing MCS scores will be imputed as non-responders within the analysis, as LOCF is not appropriate when endoscopy data, which comprises part of the MCS score, is not collected routinely.

Intercurrent events: Patients who withdraw during Study GA28951 will be set to non-responders using the composite strategy if they could have reached OLE Week 108 at the time of the clinical cut-off date had they not withdrawn from treatment. This excludes patients who withdrew from study drug with reason being stated as “study terminated by sponsor” after 15 February 2022.

Analysis 2 - As Observed

Missing data: No imputation will be performed for missing data

Intercurrent events: No imputation will be performed for treatment withdrawals

4.1.3.3 pMCS Remission

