The percentage of patients in remission defined using the pMCS will be summarized for each OLE visit for patients who entered Study GA28951. All OLE visits will be summarized until a minimum of 20 evaluable patients overall remain within the analysis (i.e., an evaluable patient either reached the visit or could have reached the visit if they had remained within the OLE).

Population: Patients who enroll into Part 1 of Study GA28951.

Baseline: The original baseline value from the parent study will be used.

Sub-groups:

- Table outputs: All patients overall, split by aTNF exposure status and by OLE Day 1 pMCS remission status.
- Figure outputs: All patients overall and split by OLE Day 1 pMCS remission status.

Analysis 1 - Hybrid LOCF

Missing data: If patients who remain in Study GA28951 at the specified visit are missing data then LOCF will be used to impute. For visits where patients are non-evaluable (i.e., it is not possible for them to have reached the specified visit at the time of the clinical cut-off date) they will be removed from the analysis.

Intercurrent Events: Using the composite strategy in the case where patients have withdrawn from the Study GA28951, they will be set to non-responders for all visits where they are evaluable. This excludes patients who withdrew from study drug with reason being stated as “study terminated by sponsor” after 15th February 2022.

Analysis 2 - As Observed

Missing data: If a patient has missing data at a visit, they will be removed from the analysis and no imputation will be performed.

Intercurrent events: No imputation will be performed for treatment withdrawals

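### Hybrid-LOCF pMCS remission: SAP 4.1.3 gives two rules for patients stopped by the sponsor after 15 February 2022, and the literal one lowers the last visits slightly

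*SAP*

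**What the plan says.** SAP 4.1.3 makes a patient evaluable at a visit from the enrolment date and the closure of Part 1, not from the patient's own stop date. Under Hybrid LOCF the rule is: "For evaluable patients with missing data, Last Observation Carried Forward (LOCF) will be used from their most recent available data".

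Under Maximum Hypothetical Evaluable Visit, a sentence that names both the hybrid-LOCF and the non-responder analyses says "this will impute patients who have withdrawn as non-responders until the 15th May 2022". It then makes an exception for patients whose recorded reason is sponsor termination after 15 February 2022: "these patients will not be imputed as non-responders and will be considered" treatment completers, with their data included as observed. The As Observed strategy in the same section reads: "No imputation will be performed for missing data or treatment withdrawals".

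SAP 4.1.3.3 (Analysis 1, Hybrid LOCF) says: "If patients who remain in Study GA28951 at the specified visit are missing data then LOCF will be used to impute". It repeats that sponsor-stopped patients are not set to non-responder, but states no rule in its place. It also sets a reporting floor: "All OLE visits will be summarized until a minimum of 20 evaluable patients overall remain within the analysis", where "an evaluable patient either reached the visit or could have reached the visit if they had remained within the OLE".

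Protocol 3.1.1.1 schedules pMCS every 12 weeks after the first three months. Appendix 1 also schedules it at the Early Withdrawal from Treatment visit, within 30 days of last dose (footnote d). Appendix 2 lists no pMCS in the 12-week safety follow-up.

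**The concern.** Take a sponsor-stopped patient with no pMCS at a visit due before 15 May 2022. The general hybrid-LOCF rule keeps this patient in with a carried-forward value. The exception, read with the SAP's own definition of as observed, removes the patient from numerator and denominator. Own-reason withdrawers stay in at the same visit as failures. Two programmers could therefore draw different remission curves from the same text.

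On the literal reading, part of any fall at the end of the long-term curve would come from closing the study. The pMCS summaries carry no test or stated interval that would alert a reader. The parallel as-observed analysis contains no imputed failures, so it cannot isolate this effect.

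**Working it through.** **Is the case real?** SAP 4.1.1 expects no patient to reach treatment completion, so everyone still on drug at termination is a potential sponsor stop. From 15 February to 15 May 2022 is 89 days and the visit interval is 84 days (89/84 = 1.06). Each such patient therefore has at least one scheduled pMCS visit in the window.

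**Direction.** The plan states no figure to reproduce. At one visit, let w be the share of evaluable patients who withdrew for their own reasons, m the share of the others with no pMCS, p the remission rate in those observed, and q the last-observed rate in those missing.

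- Carried forward: C = (1−w)[(1−m)p + mq]
- Literal: L = (1−w)(1−m)p / D, with D = 1 − (1−w)m
- Hence C − L = (1−w)·m·(q − L)

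The literal rule is lower exactly when q exceeds the pooled literal rate L. That is expected for an administrative stop, but not guaranteed. With p = 0.7, w = m = 0.5 and q = 0.1, C = 20.0% and L = 23.3%, so the sign reverses.

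**Size.** All inputs are assumptions: follow-up to 15 February 2022 uniform from 1.8 to 7.8 years (six years of even accrual), own-reason withdrawal 12% a year, on-treatment remission p = q = 70%, and sponsor stops uniform over the 89 days. With t the visit time in years and W = 89/365.25 = 0.244:

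- w = 1 − exp(−0.12t)
- Withdrawal visit not mapped to a scheduled week: m ≈ 0.5·W/(7.8 − t + W), because half of those whose visit falls in the window stop before it
- Withdrawal visit counted, up to 30 days after the stop: 0.5 becomes 0.5·(59/89)² = 0.220

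| Week | t | w | C | m, not mapped | L | gap | m, mapped | L | gap |
|---|---|---|---|---|---|---|---|---|---|
| 288 | 5.52 | 0.484 | 36.1% | 0.048 | 35.2% | 0.9 | 0.021 | 35.7% | 0.4 |
| 384 | 7.36 | 0.587 | 28.9% | 0.178 | 25.7% | 3.3 | 0.078 | 27.6% | 1.4 |
| 396 | 7.59 | 0.598 | 28.2% | 0.268 | 23.1% | 5.1 | 0.118 | 26.1% | 2.1 |

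Gaps are in percentage points, taken before rounding. Simulation with the same inputs agrees to about 0.1 point.

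**Range at Weeks 384 / 396.**

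- Withdrawal 8–18% a year and remission 60–80%: 0.9–1.6 / 1.4–2.5 mapped; 2.2–3.9 / 3.3–6.2 not mapped.
- Stops in the first third of the window: 3.3 / 5.0 mapped; 5.9 / 9.2 not mapped.
- Stops in the last third: 0 mapped; 1.0 / 1.6 not mapped.
- Accrual ramping up over one to two years: 2.7 / 3.6–3.9 mapped; about 6 / 9 not mapped.
- LOCF applied, or everyone dosed to 15 May: 0.

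**Against sampling error.** At Week 396, 2100 × 0.454/6 = 159 patients are evaluable, and 159 × 0.953 = 151 contribute in the mapped case. The SE is √(0.261 × 0.739/151) = 3.6 points. With the two-year ramp it is about 9 points; there, 22 patients meet the evaluable definition and 18 contribute when the visit is not mapped.

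**The case against.** The strongest reply is that SAP 4.1.3.3 is the endpoint-specific rule. It does not repeat as observed for Analysis 1, and its LOCF covers patients who remain in the study. The 12-week safety follow-up belongs to Part 1, so sponsor-stopped patients can be read as still remaining. LOCF would then apply and the gap would be zero. As observed in 4.1.3 may also mean only that these patients are not overwritten as failures. This stands in part. A reader might infer that 4.1.3.3 contradicts 4.1.3, but it either agrees with LOCF or leaves a gap. The clear conflict is within 4.1.3, and the SAP does not say which rule prevails.

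The early-withdrawal pMCS fills much of the hole. That stands, and the main estimate counts it. However, the SAP has no rule mapping that visit to a scheduled week, and Appendix 1 makes the score depend on available e-diary data.

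No input comes from the documents, and 2100 is a ceiling for the whole study rather than Part 1 enrolment. That stands too. The analysis is also descriptive (SAP 2.1), in a synoptic report with limited efficacy data (SAP 4).

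Two stronger readings are tempting and not supported:

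- **Earlier missed visits.** A reader might infer that the exception also cancels imputation for visits missed before the stop, including at Week 108. The endpoint rules say otherwise. SAP 4.1.3.2 states "Patients who remain in Study GA28951 but are missing MCS scores will be imputed as non-responders within the analysis", 4.1.3.1 does the same for endoscopy, and 4.1.3.3 gives LOCF.
- **A collapse at the final visit.** Under the assumed accrual, Week 408 is reachable only inside the window (7.8 years is 407 weeks), and the gap there is 11.5 points, or 4.5 with the withdrawal visit. If accrual ramps up over one to two years, only 5–10 of 2100 patients are evaluable there, below the floor of 20, so the visit is not reported.

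**Conclusion.** The concern holds as a minor drafting conflict with a predictable direction. Followed literally, the exception in SAP 4.1.3 lowers hybrid-LOCF pMCS remission at the latest visits, provided the dropped patients' last-observed remission rate exceeds the pooled rate.

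The best estimate is 1 to 2 points at Weeks 384–396 with the withdrawal visit counted, and 3 to 5 without it. In the base case it is under 1 point through Week 288. These sizes rest entirely on assumed accrual, withdrawal, remission and stop dates. The SE of about 3.6 points at Week 396 puts the size in proportion but does not remove a systematic shift. No test or hypothesis depends on the result.

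**What to change.** In SAP 4.1.3 and 4.1.3.3, replace the as-observed wording for hybrid-LOCF pMCS with one rule: patients stopped by sponsor termination after 15 February 2022 are not imputed as non-responders, and their last available pMCS, including the early-withdrawal visit, is carried forward to visits due up to 15 May 2022. This agrees with the general LOCF rule already in 4.1.3.

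Report for each visit the numbers observed, carried forward and imputed as non-responders. These counts also show how many of the patients counted toward the 20-patient floor have an observed value. Leave the Week 108 MCS and endoscopy rules as they are.

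The cost is one or two sentences and three counts per visit. The downside is a carried value for about one visit per sponsor-stopped patient, which assumes that remission status did not change after the stop. In the base case without the withdrawal visit, this affects about 17–18 of 2100 patients at each of Weeks 384 and 396.

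### pMCS remission, the only repeated efficacy endpoint, has no planned analysis that counts a missing on-treatment score as non-response

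*SAP*

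**What the plan says.** SAP 4.1.3 states that for missing data and treatment withdrawal "there will be 3 strategies employed": hybrid LOCF, as-observed and non-responder.

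- **Hybrid LOCF, general rule.** "For evaluable patients with missing data, Last Observation Carried Forward (LOCF) will be used from their most recent available data". Patients who withdrew from treatment count as non-responders up to the last visit they could have reached by 15 May 2022.
- **Non-responder, general rule.** "Evaluable patients with missing data will be set as a non-responder". This rule is also framed visit by visit, up to the last visit a patient could have reached.
- **Exception.** Patients whose stated reason for stopping after 15 February 2022 is termination by the sponsor are not made non-responders under either rule. They are treated as completers, with their data as observed.

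The endpoint sections then select from these strategies. The Week 108 endoscopic endpoints (4.1.3.1) and MCS remission (4.1.3.2) get non-responder and as-observed analyses; for MCS, "Patients who remain in Study GA28951 but are missing MCS scores will be imputed as non-responders within the analysis". pMCS remission (4.1.3.3) gets hybrid LOCF and as-observed only. In the first, "If patients who remain in Study GA28951 at the specified visit are missing data then LOCF will be used to impute", while for patients who have withdrawn "they will be set to non-responders for all visits where they are evaluable". In the second, "If a patient has missing data at a visit, they will be removed from the analysis and no imputation will be performed".

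**The concern.** Of the efficacy outcomes in SAP 1.3.1, only pMCS remission is measured repeatedly, at the early visits and then every 12 weeks. It therefore carries the claim about long-term efficacy. A non-responder rule built for successive visits is used only for endpoints assessed once, at Week 108, and is left out where there are successive visits.

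The missingness at issue may be informative. Stool frequency and rectal bleeding come from e-diary entries. Under Protocol 3.1.1.1, patients with worsening disease may receive corticosteroids, 5-ASA or immunosuppressants and stay on etrolizumab, so the withdrawal rule does not catch them. If such a patient has no score at a visit, an earlier remission can stand in for it. The earlier value may even be the Week 0 score. SAP 1.3.1 lists Week 0 as a pMCS assessment, and Protocol Appendix 1 takes that score from the final parent-study visit. Among patients in remission on OLE Day 1, a subgroup that 4.1.3.3 reports separately, a carried Week 0 value is a remission by construction.

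At stake is how far the reported remission percentages rest on carried values. No test or error rate is affected, because the study is descriptive.

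**Working it through.** The plan states no figure to reproduce. The check compares the three rules algebraically at one visit.

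**Notation.** Take the n evaluable patients at a visit, setting aside those stopped by sponsor termination.

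- w = withdrawn; m = on treatment but with no score; o = n − w − m = observed
- x = remitters among the observed; c = remitters among the m carried-forward values

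Assume no score recorded after withdrawal enters the as-observed count.

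**Formulas.**

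- Hybrid LOCF = (x + c)/n
- As-observed = x/o
- Non-responder = x/n

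Since c ≥ 0 and o ≤ n, both planned figures are always at or above x/n. This follows from the definitions: counting every missing score as failure gives the lowest possible figure. It shows that neither planned analysis can act as the lower bound. It does not show that either exceeds the true rate.

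**Gap between hybrid LOCF and non-responder.** The difference is c/n = (m/n) × (c/m). The denominator of the first factor is all evaluable patients, including those withdrawn. The documents give neither factor, so the values below are assumptions. The gap is in percentage points.

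| m/n | c/m = 40% | c/m = 60% | c/m = 80% |
|---|---|---|---|
| 2% | 0.8 | 1.2 | 1.6 |
| 5% | 2.0 | 3.0 | 4.0 |
| 10% | 4.0 | 6.0 | 8.0 |
| 20% | 8.0 | 12.0 | 16.0 |

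If 40% have withdrawn and 10% of those retained are missing, m/n is 0.60 × 0.10 = 6%, not 10%. At 60% carried remission the gap is then 3.6 points.

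**All three figures together (assumed values).** With w/n = 40%, m/n = 10%, and 60% remission among both observed and carried values, o/n = 50%.

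- Non-responder: 0.50 × 0.60 = 30.0%
- Hybrid LOCF: 30.0% + 0.10 × 0.60 = 36.0%
- As-observed: 60.0%

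Most of the distance between as-observed and non-responder here comes from withdrawals. Only the 6 points between hybrid LOCF and non-responder come from on-treatment missing scores.

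**Small denominators.** Section 4.1.3.3 reports visits down to 20 evaluable patients. There, one carried remission adds 1/20 = 5 points.

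**Length of carry.** Over the protocol's ceiling of about 9 years there are 9 × 365.25 / 7 / 12 ≈ 39 twelve-week intervals. No rule limits how many one value may fill. This describes the rule and does not forecast how long values will be carried.

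**The case against.** The strongest reply is that the plan is internally consistent and already conservative where it matters most. Much of this stands.

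- **No contradiction.** A reader might infer that announcing three strategies and giving pMCS two is an inconsistency. It is not: all three are used somewhere in 4.1.3, and nothing promises all three for each endpoint. Nor does the SAP's reason for refusing LOCF at Week 108, that endoscopy is not collected routinely, apply to pMCS.
- **Withdrawals are covered.** A reader might take the LOCF analysis to carry remission forward after patients stop treatment. It does not, apart from the stated sponsor-termination exception. Patients given prohibited rescue therapy stop etrolizumab and so become non-responders. Missing scheduled visits is itself a listed reason for discontinuation (Protocol 4.5.1). The gap concerns only retained patients without a score.
- **Overstatement is not shown.** A reader might infer that both pMCS analyses overstate durability. LOCF carries non-remission as well. Many patients enter after non-response, relapse or rescue, and for those not in remission on Day 1 a carried Week 0 value counts as failure.
- **Long carries may be rare.** The score uses only the three most recent diary entries, diary failure has a telephone back-up, and pMCS is also required when disease worsens (Protocol Appendix 5). The first four doses are given in clinic, with pMCS scheduled at Weeks 4, 8 and 12, so carrying Week 0 through Week 12 needs three successive missing scores.
- **The bound may be recoverable.** If counts are printed, observed remitters from the as-observed table over evaluable patients from the hybrid table approximates x/n.

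What remains is that 4.1.3.3 speaks of percentages and does not say that these counts will be shown. Even if they are, the reader must combine two tables and assume no post-withdrawal scores are included. The number and age of carried values stay hidden.

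**Conclusion.** The point holds as a gap in the analysis of pMCS remission. Neither planned analysis counts an on-treatment missing score as non-response, so the only repeated efficacy endpoint has no reported lower bound for that kind of missingness. Hybrid LOCF is not wrong in itself here, and the direction of any bias against the true remission rate is unknown.

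The size is exact as a formula and assumed as a number: about 1 to 16 percentage points per visit for 2% to 20% missing and 40% to 80% carried remission. If on-treatment missingness is low, the gap is negligible, and the added analysis would show that. With descriptive reporting and a synoptic CSR containing limited efficacy data, this is an inexpensive improvement and not a flaw that invalidates the plan.

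**What to change.** Add an Analysis 3 (Non-responder) to SAP 4.1.3.3 as a sensitivity analysis. Use the rule already in 4.1.3 and keep the existing exception for sponsor-terminated patients. At each visit, report the number of patients whose value is carried forward and how many of those carry a Week 0 score.

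Leave hybrid LOCF as Analysis 1. A carry-forward limit is optional. Any particular limit is a judgement the documents do not settle, and a limit or a bar on Week 0 would rewrite Analysis 1. A bar on Week 0 would also need a rule for a missing Week 4 score with no earlier OLE value.

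The cost is one extra table from a rule already defined, with no new data, plus the carried-value counts. The downside is a lower remission figure (or at most an equal one) printed beside the main one.
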